## 15.4                    Vital Signs

Weight will be collected at Baseline when available. It will be summarized descriptively.

Unit conversion:

Weight (kg) = 0.4536 \* weight (lb)

## 15.5

## Other Safety or Tolerability Evaluations

Physical examination, as per the standard of care, will be performed at Baseline. The number and percentage of patients completing the physical examination will be reported.

Neurological examination, as per standard of care, will be performed at Baseline and at Visits 2, 3, 5, and 6. During the examination, if Kurtzke Functional System Scores (FSS), ambulation up to 500 meters, and Expanded Disability Status Score are collected as standard of care, they will be reported and evaluated. No imputation will be performed if any items in the above examinations are missing. Visit values (including Baseline) and changes from baseline values will be considered. All the items will be summarized descriptively.

## 16

## Analyses of Other Endpoints

CCI

[REDACTED]

[REDACTED]

[REDACTED]

### 16.3

### Patient-Reported Outcome

Analysis (Analysis Population)	Derivation	Statistical Analysis Methods	Missing Data Handling
Secondary Endpoints: ePROs			
Secondary (FAS)	Scores collected at Baseline and at Months 6, 12, and 24 for the following PROs (TSQM, SF-36, MFIS-5, BDI-FS, WPAI-MS)	Baseline scores and change from baseline scores will be summarized descriptively	See description in section 16.3
	Scores collected at Baseline and at Months 6, 12, and 24 for PDDS	Baseline scores and change from baseline scores will be summarized descriptively	See description in section 16.3

BDI-FS: Beck-Depression Inventory-Fast Screen; ePROs: electronic patient-reported outcomes; FAS: Full Analysis Set; MFIS-5: Modified Fatigue Impact Scale – 5-Item Version; PDDS: Patient Determined Disease Steps; PRO: Patient-reported outcome; SF-36: 36-Item Short Form Health Survey; TSQM: Treatment Satisfaction Questionnaire for Medication; WPAI-MS: Work Productivity Activity Impairment-Multiple Sclerosis

### TSQM

TSQM-1.4 is an instrument to assess patient satisfaction with medications, providing scores on 4 scales: side effects, effectiveness, convenience, and global satisfaction. With the exception of item (i.e., question) 4 (presence of side effects; yes or no), all items have 5 or 7 responses, scored

from 1 (least satisfied) to 5 or 7 (most satisfied). Higher scores indicate higher satisfaction. Scores for each domain are computed by adding the TSQM items in each domain and then transforming the composite score into a value ranging from 0 to 100. Of note, a score can be computed for a domain only if no more than one item is missing from that domain. The calculations specific to each domain are presented in detail below.

*Global Satisfaction*

$([(\text{Sum (Item 12 to Item 14)}) - 3] \text{ divided by } 14) * 100$

If Item 12 or 13 is missing:

$([(\text{Sum (the 2 completed items)}) - 2] \text{ divided by } 10) * 100$

If Item 14 is missing:

$([(\text{Sum (Item 12 and Item 13)}) - 2] \text{ divided by } 8) * 100$

*Effectiveness*

$([(\text{Item 1} + \text{Item 2} + \text{Item 3}) - 3] \text{ divided by } 18) * 100$

If one item is missing:

$([\text{Sum (the 2 completed items)}) - 2] \text{ divided by } 12) * 100$

*Side Effects*

If Question 4 is answered “No,” then score = 100

Else

$([\text{Sum (Item 5 to Item 8)} - 4] \text{ divided by } 16) * 100$

If one item is missing:

$([(\text{Sum (the 3 completed items)}) - 3] \text{ divided by } 12) * 100$

*Convenience*

$([\text{Sum (Item 9 to Item 11)} - 3] \text{ divided by } 18) * 100$

If one item is missing:

$([(\text{Sum (the 2 completed items)}) - 2] \text{ divided by } 12) * 100$

The 14 items are listed in the Appendices.

Each derived score will be summarized descriptively as a continuous variable.

## **SF-36**

SF-36 is a self-administered, generic health status questionnaire consisting of 36 questions that measure 8 health concepts: physical functioning, role limitations due to physical problems, bodily pain, general health perception, vitality, social functioning, role limitations due to emotional problems, and mental health (MH).

The SF-36 has a single item covering change in health status over the last year and 8 multi-item scales. Two summary scales (Physical and Mental) have also been derived using factor analytic methods. Scales are set up, with higher scores indicating better health.

The SF-36 questionnaire is reported in the Appendices.

The reference tool for the derivation of the composite scores will be the scoring software provided by Optum, PRO CoRE: SF-36v2.

The algorithm used by this software has 5 steps for the scoring of the profile scales:

1. Data Cleaning and Item Recoding
2. Item Recalibration
3. Computation of Raw Scores
4. Transformation of Raw Scale Scores to 0-100 Scores
5. Transformation of 0-100 Scores to T-score Based Scores

After these steps, the component summary measures are derived as follows:

1. Standardization of the SF-36v2® Health Survey Scales
2. Aggregation of the Scale Scores
3. Transformation of Summary Scores

Details for the above steps are included in the manual provided with the software.

Missing items can be replaced using Maximum Data Recovery (Max). With this method, the software applies a value to a scale item rendered missing if at least one of the items in that scale has valid data. A scale receives a “missing” score (“.”) only if all the items in that scale are missing. Physical Components Summary Score (PCS) and Mental Component Summary Score (MCS) are calculated when at least 7 of the 8 profile scales have valid data, either actual or estimated.

However, to calculate PCS, the Physical Function (PF) scale must be one of the 7 scales with valid data. Also, to calculate MCS, the MH scale must be one of the 7 scales with valid data.

## MFIS-5

MFIS-5 is a modified form of the Fatigue Impact Scale that consists of 5 questions that assess the impact of fatigue on physical, cognitive, and psychosocial functioning, with 5 response levels ranging from 0 ("Never") to 4 ("Almost always"). Total scores range from 0 to 20, with higher scores representing a greater impact of fatigue.

Consider the following scale: 0 (Never), 1 (Rarely), 2 (Sometimes), 3 (Often), and 4 (Almost always).

The following items from the MFIS constitute the MFIS-5:

- I have been less alert.
- I have been limited in my ability to do things away from home.
- I have had trouble maintaining the physical effort for long periods.
- I have been less able to complete tasks that require physical effort.

- I have had trouble concentrating.

Each item (and the total score) will be summarized descriptively considering the raw scores as values of a continuous variable.

No imputation will be performed if any items in the MFIS-5 are missing.

### **BDI-FS**

The 7-item BDI-FS is a self-report inventory for measuring the severity of depression on a 7-item scale. The BDI-Fast Screen is scored by summing all of the highest ratings for each of the 7 items. Each item is rated on a 4-point scale ranging from 0 to 3. The maximum total score is 21. Higher scores indicate greater symptom severity. If an examinee has multiple endorsements for an item, the statement with the highest rating should be scored.

The 7 items are as follows: Sadness, Pessimism, Past Failure, Loss of Pleasure, Self-Dislike, Self-Criticalness, and Suicidal Thoughts.

Each item (and the total score) will be summarized descriptively, considering the raw scores as values of a continuous variable.

No imputation will be performed if any items in the BDI-FS are missing.

### **WPAI-MS**

The WPAI-MS questionnaire is a 6-item validated instrument to measure impairment in work and activities. The WPAI yields 4 types of scores: 1. Absenteeism (work time missed); 2. Presenteeism (impairment at work/reduced on-the-job effectiveness); 3. Work productivity loss (overall work impairment/absenteeism plus presenteeism); and 4. Activity impairment. WPAI outcomes are expressed as impairment percentages, with higher numbers indicating greater impairment and less productivity.

WPAI outcomes are expressed as impairment percentages, with higher numbers indicating greater impairment and less productivity, i.e., worse outcomes, as follows:

#### Questions:

- 1 = Are you currently employed (working for pay)?
- 2 = During the past 7 days, how many hours did you miss from work because of problems associated with your multiple sclerosis (MS)?
- 3 = During the past 7 days, how many hours did you miss from work because of any other reason, such as vacation, holidays, time off to participate in this study?
- 4 = During the past 7 days, how many hours did you actually work?
- 5 = During the past 7 days, how much did your MS affect your productivity while you were working? (Scale 0-10)
- 6 = During the past 7 days, how much did your MS affect your ability to do your regular daily activities, other than work at a job? (Scale 0-10)

#### Scores:

Multiply scores by 100 to express in percentages.

1. Percent work time missed due to health:  $Q2/(Q2+Q4)$
2. Percent impairment while working due to health:  $Q5/10$
3. Percent overall work impairment due to health:  $Q2/(Q2+Q4)+[(1-(Q2/(Q2+Q4)))\times(Q5/10)]$
4. Percent activity impairment due to health:  $Q6/10$

Each score (percentage) will be summarized descriptively as a continuous variable.

No imputation will be performed if any items in the WPAI-MS are missing.

### **PDDS**

The PDDS is a patient-reported scale to assess the disability status in patients with MS, and it focuses mainly on how patients walk. A higher score represents a higher level of disability. Scores on the PDDS range from 0 (normal) to 8 (bedridden): 0 (Normal), 1 (Mild Disability), 2 (Moderate Disability), 3 (Gait Disability), 4 (Early Cane), 5 (Late Cane), 6 (Bilateral Support), 7 (Wheelchair/Scooter), and 8 (Bedridden).

This single item will be summarized descriptively as a continuous variable using raw scores.

No imputation will be performed if any values in the PDDS are missing.

## 16.4                    Treatment Adherence

Analysis (Analysis Population)	Derivation	Statistical Analysis Methods	Missing Data Handling
secondary Endpoint: Treatment adherence			
Secondary (FAS)	Treatment adherence based on modified versions of the MS-TAQ. Data collected at baseline and at Months 1, 2, 13, and 14	Baseline scores over time will be summarized descriptively	See description in Section 16.4

FAS: full analysis set; MS-TAQ: Multiple Sclerosis Treatment Adherence Questionnaire

### Treatment Adherence Questions

Seven treatment adherence questions, based on modified versions of the MS-TAQ, were developed to determine adherence and identify barriers to adherence for MS patients taking DMDs. A version of the MS-TAQ has been modified for once- or twice-daily oral dosing to assess adherence to the last previous oral DMD treatment at Baseline. Another version of the MS-TAQ has been modified to assess adherence to the last previous infused DMD treatment at Baseline. Finally, a version has been modified for cladribine tablets to assess adherence to cladribine tablets throughout the study.

For these versions, the single questions will be summarized descriptively. Items on an ordinal scale will be summarized as continuous variables. No imputation will be performed if any values in the MS-TAQ are missing.

The 3 modified versions of the MS-TAQ are reported in the Appendices.

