2.) During the last 4 weeks (28 days) that you were taking this medication, how many days were you supposed to take this medication? (Check one)

Twice a day (58 times)	
Once a day (28 times)	
Other, please specify:	

3.) Did you miss or forget to take any doses of this medication during the last 4 weeks (28 days) that you were taking the medication? (Check one)

Yes	
No	

4.) How many doses did you miss or forget to take? (Complete blank)

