**MS-TAQ Modified version to assess adherence during last previous infused DMD treatment**

1.) Before enrolling in this study, what infused/intravenous (IV) medication you were taking to treat Multiple Sclerosis (MS)? (Check one)

Tysabri (natalizumab)	
Ocrevus (ocrelizumab)	
Lemtrada (alemtuzumab)	

2.) During the time that you were taking this medication, how often in the past year (or the time that you were taking this medication if less than one year) were you supposed to take this medication? (Check one). If none of the choices below describe your exact dosing, please describe under Other.

Tysabri - Every 4 weeks	
Ocrevus - 1st month doses only	
Ocrevus - 1st month and 6-month doses	
Lemtrada - 5 days per year (1st year)	
Lemtrada - 3 days per year (subsequent years)	
Other, please specify:	

3.) Did you miss or forget to take any doses of this medication during the past year (or the time that you were taking this medication if less than one year)? (Check one)

Yes	
No	

4.) How many doses did you miss or forget to take? (Complete blank)

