**MS-TAQ modified for cladribine tablets**

1.) What treatment week of cladribine tablets did you most recently complete? (check one)

Year 1, Treatment Week 1	
Year 1, Treatment Week 2	
Year 2, Treatment Week 1	
Year 2, Treatment Week 2	
Other, please specify:	

2.) How many cladribine tablets were you supposed to take during this treatment week?  
(complete the blank)

3.) Did you miss or forget to take any cladribine tablets during this treatment week?  
(Check one)

Yes	
No	

4.) How many cladribine tablets did you miss or forget to take? (Complete blank)

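### The SAP reports MS-TAQ adherence only as single items, with no missed-to-scheduled rate, so its missed-dose results cannot be read as adherence across the three versions or pooled within the oral or infusion version

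*SAP*

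**What the plan says.** Adherence during cladribine treatment is a secondary objective (Protocol 8.2; SAP Section 5). The table in SAP 16.4 gives the method as "Baseline scores over time will be summarized descriptively", but the section defines no score. The text below it says "For these versions, the single questions will be summarized descriptively" and adds "No imputation will be performed if any values in the MS-TAQ are missing".

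The three forms in SAP Section 18 ask about missed doses over different periods:

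- Oral DMDs: "Did you miss or forget to take any doses of this medication during the last 4 weeks (28 days". Item 2 offers once daily (28 times) or "Twice a day (58 times".
- Infusion DMDs: "Did you miss or forget to take any doses of this medication during the past year", or the time on drug if that is shorter. Item 2 records a schedule category, not a count.
- Cladribine: "Did you miss or forget to take any cladribine tablets during this treatment week". Item 2 asks how many tablets were due.

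Item 4 of each form asks for the number missed. SAP Section 13 separately defines cladribine compliance as actual over planned tablets from the exposure eCRF pages, and summarises the percentage of planned doses received. It refers the adherence endpoint itself to 16.4.

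**The concern.** Item 3 (any dose missed) and item 4 (number missed) both grow with the number of doses a patient could have missed. That number differs by design between the forms and, for oral and infusion DMDs, within a form. Two groups with the same per-dose adherence will give different results on both items.

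The baseline table describes adherence to the last DMD, and the tables for Months 1, 2, 13 and 14 describe cladribine. Poor adherence to the previous DMD is one of the qualifying reasons for entry (Protocol 9.2.1), so readers will naturally look from one table to the other. They could take a difference in scheduled doses for a difference in behaviour. The baseline table is also hard to read alone, because it pools once-daily with twice-daily patients, and frequent with infrequent infusions.

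**Working it through.** **Printed count.** The oral form's window is "During the last 4 weeks (28 days) that you were taking this medication". Once daily gives 28 x 1 = 28, as printed. Twice daily gives 28 x 2 = 56, not 58; 58 would need 29 days. The overstatement is 2/56 = 3.6%.

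**Inputs.** Scheduled doses n:

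- Oral: 28 or 56.
- Cladribine: 4 or 5 dosing days per treatment week (Protocol 9.2.2). In tablets this is about 4 (at 41-49 kg) to 10 per week by the SAP Section 13 formula.
- Infusion: about 13 a year if every 4 weeks (365/28). The other schedules imply a few; 2 and 3 are used here as examples.

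The per-dose miss probability p is not in the documents. It is an assumption, shown from 1% to 20%.

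**Any dose missed, independent doses.** P = 1 - (1 - p)^n, with the same p everywhere:

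| p | Cladribine, n = 5 | Once daily, n = 28 | Ratio | Twice daily, n = 56 | Ratio |
|---|---|---|---|---|---|
| 1% | 4.9% | 24.5% | 5.00 | 43.0% | 8.78 |
| 2% | 9.6% | 43.2% | 4.50 | 67.7% | 7.05 |
| 5% | 22.6% | 76.2% | 3.37 | 94.3% | 4.17 |
| 10% | 41.0% | 94.8% | 2.31 | 99.7% | 2.44 |
| 20% | 67.2% | 99.8% | 1.48 | 100.0% | 1.49 |

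If each of 10 tablets counts as a separate opportunity, the ratios at 1-5% fall to 1.90-2.57 (once daily) and 2.35-4.50 (twice daily).

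**Patient heterogeneity.** A beta-binomial model with mean miss rate m = 2-10% and intraclass correlation r = 0.05-0.4 was used: s = 1/r - 1, a = ms, b = (1 - m)s, and P(none missed) = B(a, b + n)/B(a, b). At m = 2%, r = 0.05 the any-missed figures for n = 5, 28 and 56 are 8.8%, 29.7% and 41.3% (ratios 3.39 and 4.71). At m = 10%, r = 0.4 they are 23.9%, 40.0% and 45.8% (ratios 1.68 and 1.92). The full range is 1.7-3.4 for once daily and 1.9-4.7 for twice daily.

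**Infusions, p = 2%.** Thirteen infusions give 23.1%, which is 2.4 times the cladribine 9.6%. Two or three give 4.0-5.9%, which is 0.4-0.6 times. The direction reverses.

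**Within one form, p = 2%.** Oral patients show 43.2% or 67.7% depending on schedule. Infusion patients show 4.0% (n = 2) or 23.1% (n = 13).

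**Mean number missed.** This is np, so the oral-to-cladribine ratio does not depend on p: 28/5 = 5.6 up to 56/4 = 14, or 28/10 = 2.8 at the low end in tablets.

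**Effect of a rate.** The expected value of 100 x (scheduled - missed)/scheduled is 100(1 - p) for any n, for example 95% at p = 5% for n = 5, 28 or 56. Using 58 in place of 56 would move it little: 3 missed gives 94.83% against 94.64%, and 6 missed gives 89.66% against 89.29%.

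**Item 4 when item 3 is No.** The skip instruction comes after item 4 in all three forms, so a patient who missed nothing may enter 0 or leave it blank. At the extreme, if 10 of 100 patients miss 3 doses each and the other 90 leave it blank, the item 4 mean is 30/10 = 3.0 on n = 10; with zeros it is 30/100 = 0.3.

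**The case against.** The best defence is that the plan never compares prior-DMD with cladribine adherence. The objective concerns adherence during cladribine treatment. SAP Section 5 restricts the prior-DMD questionnaire to baseline scores and the cladribine questionnaire to scores at each time point, with no change from baseline. This stands, and it confines the harm to how the tables are read. It does not rescue the pooled baseline items, which mix different dose counts within a form.

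A reader might infer that the SAP contains no adherence rate at all. It does: Section 13 gives cladribine compliance and percentage of planned doses. That measure comes from the eCRF, covers cladribine only, and is kept apart from the questionnaire endpoint. The gap is a rate from the MS-TAQ, and any rate for prior DMDs.

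A reader might also infer that the tables will show a large adherence gain on cladribine. The documents do not support this. They give no miss rate, the ratio shrinks at higher miss rates and with heterogeneity, and the direction reverses against sparse infusions. That reversal matters here, since Protocol 9.2.2 plans about 100 patients switching directly from ocrelizumab.

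Two smaller inferences also go too far. No planned analysis divides by 58, so it is a misprint with no effect on results. Blank item 4 answers are possible, not certain, and SAP Section 9 requires missing counts to be shown, so a reduced n would be visible.

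**Conclusion.** The point holds in a limited form. The MS-TAQ missed-dose items, as planned, are not adherence measures that can be compared across versions or pooled within the oral or infusion version.

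Against 5 cladribine doses, equal per-dose adherence gives an any-missed proportion about 3-9 times higher on daily oral DMDs at miss rates of 1-5%, and about 1.5-2.4 times at 10-20%, assuming independent doses. With patient heterogeneity the range is 1.7-4.7. Against 2-3 infusions the cladribine figure is the higher one. All these sizes rest on an assumed common miss rate and on counting dosing days; counting tablets makes them smaller. What needs no assumed rate is that the scheduled-dose counts differ and that no questionnaire rate corrects for this.

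The consequence is a risk of misinterpretation in a descriptive secondary endpoint. The primary endpoint is not affected.

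**What to change.** In SAP 16.4:

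1. Derive adherence % = 100 x (scheduled - missed)/scheduled for each form. Use 28 or 56 (not 58) for oral DMDs and the item 2 tablet count for cladribine. For infusions, count those due within the recall window from the item 2 schedule and the DMD start and stop dates already collected (Protocol 9.3). The schedule category alone is not enough, because the window shortens with time on drug and one prior infusion suffices for entry. Where the number due cannot be determined, set the rate to missing.
2. Set item 4 to 0 when item 3 is No, and state that this is a logical derivation, not imputation.
3. Report the rate at baseline by DMD route and at Months 1, 2, 13 and 14, next to the Section 13 compliance percentage.
4. Keep items 3 and 4 as supporting results, labelled not comparable across versions or dosing schedules.

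The cost is SAP text and one derived variable, with no new data. Some infusion patients may have no computable rate, and their number should be shown.

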## 17                    References

No references.

## 18                    Appendices

### TSQM items

1. How satisfied or dissatisfied are you with the ability of the medication to prevent or treat your condition?  
(Score 1 to 7)
2. How satisfied or dissatisfied are you with the way the medication relieves your symptoms?  
(Score 1 to 7)
3. How satisfied or dissatisfied are you with the amount of time it takes the medication to start working?  
(Score 1 to 7)
4. As a result of taking this medication, do you currently experience any side effects at all?

(Score 0[No] or 1[Yes])

5. How bothersome are the side effects of the medication you take to treat your condition?

(Score 1 to 5)

6. To what extent do the side effects interfere with your physical health and ability to function (i.e., strength, energy level, etc.)?

(Score 1 to 5)

7. To what extent do the side effects interfere with your mental function (i.e., ability to think clearly, stay awake, etc.)?

(Score 1 to 5)

8. To what degree have medication side effects affected your overall satisfaction with the medication?

(Score 1 to 5)

9. How easy or difficult is it to use the medication in its current form?

(Score 1 to 7)

10. How easy or difficult is it to plan when you will use the medication each time?

(Score 1 to 7)

11. How convenient or inconvenient is it to take the medication as instructed?

(Score 1 to 7)

12. Overall, how confident are you that taking this medication is a good thing for you?

(Score 1 to 5)

13. How certain are you that the good things about your medication outweigh the bad things?

(Score 1 to 5)

14. Taking all things into account, how satisfied or dissatisfied are you with this medication?

(Score 1 to 7)

